3.4 Table of endpoints/outcomes

Objectives	Outcome Measures	Timepoint(s) of evaluation of this outcome measure (if applicable)
Primary Objective: To measure the effect of a 3-month NMES programme on muscle strength, the core manifestation of sarcopenia, compared with standard care for HD patients	Isometric strength	Screening visit (as a familiarisation session), baseline, 3, 6, 9 months post randomisation
Secondary Objectives To measure the effect of a NMES programme on QoL	The Kidney Disease Quality of Life tool (KDQoL)	Baseline, 3, 6, 9 months post randomisation
To evaluate the cost-effectiveness of a NMES programme compared with standard care for patients with end-stage kidney disease within an NHS costing perspective – health economic evaluation	EQ-5D-5L questionnaire Resource use questionnaire	Baseline, 3, 6, 9 months post randomisation
To measure the effect of a NMES programme on muscle size and measures of physical function	Muscle mass (thickness and cross- sectional area by ultrasound) Muscle quality and architecture (e.g. echo intensity and angle of pennation by ultrasound)	Baseline, 3, 6, 9 months post randomisation
	Handgrip strength by dynamometry	
	Lower-extremity strength, functional capacity, and balance (using the short physical performance battery (SPPB)) and Sit to stand 60.	
	Cardiovascular functional capacity and endurance (by the 6-minute walk test or the ISWT if space constraints)	
	Body composition (using bioelectrical impedance)	
	Muscle endurance (using the Sit-to- stand-60 test muscle endurance)	
	Isometric rate of force development	
	Physical activity levels (using GP Physical Activity questionnaire and accelerometry)	

To investigate if NMES results in neuromuscular adaptations and changes in muscle phenotype	Levels of fatigue (using SONG-HD score) Perception of muscle function (using the SarQoL questionnaire) Indices of sarcopenia (using the SARC-F questionnaire). Motor unit recruitment, and discharge rate, and conduction velocity (using high density electromyography) Motor unit potential jiggle and segment jitter (using intramuscular electromyography) Evoked quadriceps contractile properties Skeletal muscle biopsy analysis	Baseline, 3-months post randomisation.
To measure the safety of the intervention	Adverse Events relating to the intervention	3-months post randomisation

4. STUDY DESIGN

STIM-HD is a prospective, open-label, assessor blind, two-arm, multi-centre, randomised controlled trial. Assessments will be made at baseline and at 3-months post randomisation (i.e. at the end of the intervention period) and at -6 and -9 months post randomisation.

In total, 228 participants (114 per arm, adults with end-stage kidney disease and sarcopenia, who are receiving long-term haemodialysis either in hospital, or at home) will be recruited and randomised to receive either 3-months of NMES or standard care. In addition, 50 participants (25 in each arm) will also take part in the neuromuscular assessments (high-density surface and intramuscular electromyography and 24 participants (12 per arm) for a skeletal muscle biopsy.

Participants will be recruited from 5 hospital and satellite haemodialysis centres from 3 NHS Trusts across the east and west midlands.

5. STUDY SETTING

STIM-HD will be run as a multi-centre study in secondary care across University Hospitals of Leicester NHS Trust (UHL), University Hospitals Coventry and Warwickshire (UHCW) and University Hospitals Birmingham NHS Foundation Trust (UHB).

6. PARTICIPANT ELIGIBILITY CRITERIA

6.1 Inclusion criteria

- 1. Undertaking HD for >3-months (home or unit based)
- 2. Age >18 years
- 3. Has sarcopenia diagnosed by low muscle strength on patient screening (<27kg for men and <16kg for women for handgrip strength)
- 4. Able to give written informed consent

6.2 Exclusion criteria

- 1. Contra-indications to neuromuscular electrical stimulation therapy including:
 - i. Lower limb amputation
 - ii. Active skin ulceration or infection
 - iii. Symptomatic lower limb claudication/ ischaemia
 - iv. Lower limb deep vein thrombosis <3-months
 - v. Cardiac pacemaker or implantable cardiac defibrillator
 - vi. Metallic hip or knee joint
- 2. Conditions known to cause muscle wasting
 - i. Known neuromuscular disease
 - ii. Active malignancy
- Scheduled for living donor kidney transplant or plan to change dialysis modality or centre in the next 6months
- 4. Life expectancy of <6-months
- 5. Current participation in an interventional trial with conflicting therapies or outcomes
- 6. Unable to give written informed consent.

Muscle biopsy and intramuscular electromyography specific exclusion criteria

- 1. On anti-coagulation (e.g. warfarin / Direct Oral Anticoagulant)
- 2. Bleeding disorder (e.g. haemophilia)
- 3. On high dose statins (i.e. atorvastatin 80mg), growth hormone or steroids.
- 4. Deep vein thrombosis

Bioelectrical Impedance specific exclusion criteria

1. Has a pacemaker

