4.2 Exclusion criteria

- 1) Contraindications to neuromuscular electrical stimulation
 - Lower limb amputation
 - Active skin ulceration or infection
 - Symptomatic lower limb claudication/ischaemia
 - Lower limb deep vein thrombosis <3 months
 - Cardiac pacemaker or implantable cardiac defibrillator

IRAS: 347115

- The presence of metallic material in/around the hips or knees.
- 2) Conditions known to cause muscle wasting
 - Known neuromuscular disease
 - Active malignancy
- 3) Scheduled for living donor kidney transplant or plan to change dialysis modality and/or centre in the next 3 months
- 4) Pregnancy or planning to become pregnant during the course of the study
- 5) Life expectancy <6 months
- 6) Current participation in a study with conflicting therapies/outcomes
- 7) Unable to consent

5 Study Schedule

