14.4 Assessment and management of risk

The main risks involved in this study are:

 Tests of physical function: As with all exercise there is a small risk of injury. All tests will be carried out by a trained member of the team and explained and demonstrated to all participants. Before the test is carried out, participants will undergo a familiarisation test where they can practice and get used to how the test

feels. All the tests that we have included here are routinely used in long-term conditions, and they will all be carried out in a hospital setting.

- 2. NMES procedure: This evokes a muscle contraction, so it is likely that following the first few sessions especially, participants will feel sore afterwards, much like when you have lifted weights after having not done this exercise for a while. This soreness will likely last a day or two at the start of the programme, but is not due to damage to the muscle, but is the normal response to having performed unaccustomed exercise.
- 3. Intramuscular electromyography: Intramuscular EMG involves inserting a thin needle (similar size to acupuncture) into the muscle during low level contractions. Intramuscular EMG is a routine clinical procedure with reports of complications being very rare. The possibility of bleeding is very low, and occasionally bruising around the insertion site is possible though rare. We have used this technique several times before in clinical populations with no adverse events (IRAS IDs: 22569, 306712, 321959)
- 4. Femoral nerve stimulation: stimulation of the femoral nerve can result in some brief discomfort in the area under the stimulating (cathode) electrode due to local skin receptor activation and this effect is usually perceived as a tingling sensation that accompanies involuntary muscle twitch contractions. This discomfort disappears as soon as the stimulation ceases (1 ms pulse). Familiarisation will be performed to minimise discomfort and participants will be monitored throughout this procedure to ensure that discomfort is not excessive. There are rare reports of the stimulation interfering with implantable devices and rare reports of skin burns; therefore, participants with a pacemaker or a similar device, and participants with metal objects around the area of stimulation (i.e., in/around the hip joint) will be excluded.

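### RCT section 14.4 excludes people with metal in or around the hip because of femoral nerve stimulation, but no criterion in section 6 carries that exclusion and its scope is not stated

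*Protocol*

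**What the plan says.** All sections cited are in the RCT protocol unless WP1 is named.

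- **Section 6.2** opens its first exclusion with "Contra-indications to neuromuscular electrical stimulation therapy including". Under it stand "Cardiac pacemaker or implantable cardiac defibrillator" and "Metallic hip or knee joint".
- The same section then adds lists for single procedures. One is headed "Muscle biopsy and intramuscular electromyography specific exclusion criteria" and another covers bioelectrical impedance. There is none for femoral nerve stimulation.
- **Section 14.4, item 4**, is about femoral nerve stimulation. It begins by noting that "stimulation of the femoral nerve can result in some brief discomfort in the area under the stimulating (cathode) electrode". It goes on to rare interference with implants and rare skin burns, and concludes that "participants with a pacemaker or a similar device, and participants with metal objects around the area of stimulation" will be excluded. A bracket limits that area to the hip joint and its surroundings.
- **Section 8.8** makes femoral nerve stimulation item 4 of an optional mechanistic study. It is done in some centres only, and people may join the main study without it.
- **Sections 7.1 and 7.2** give evoked contractions by femoral nerve stimulation their own row in both arms, with a familiarisation at screening and measurements at baseline and 3 months. The biopsy and EMG rows are marked optional. This row is not.

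**The concern.** Section 8.1 has the clinical team identify patients from the inclusion and exclusion criteria. A safeguard that appears only in a risk narrative does not reach that step. Section 14.4 relies on an exclusion to manage two named hazards, but the eligibility section does not contain it in full. Nor does the protocol say what a person with such metal is excluded from.

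At stake is a participant-safety statement, not an estimate. A site that follows section 6 and the visit schedule could deliver femoral nerve stimulation, possibly already at the screening familiarisation, to someone whom 14.4 says is excluded. Sites in three Trusts could also decide differently about the same kind of patient.

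**Working it through.** No figure in the plan depends on this, so there is nothing to recompute. The check sets the sections side by side.

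| Item | Section 6.2 | Section 14.4, item 4 | Match? |
|---|---|---|---|
| Metallic hip joint | named | covered | yes |
| Metal in or around the hip that is not a joint | not named | excluded | **no** |
| Metallic knee joint | named | not mentioned | no conflict; 6.2 is the wider text here |
| Pacemaker | named | excluded | yes |
| Implantable cardiac defibrillator | named | presumably one of the similar devices | yes, on that reading |
| Any other implanted device resembling a pacemaker | not named | depends on how 14.4 is read | **unclear** |

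1. **Does another part of section 6 close the metal gap?** No. The biopsy and intramuscular EMG list concerns anticoagulation, bleeding disorder, certain drugs and deep vein thrombosis. The bioimpedance list repeats the pacemaker, although 6.2 already excludes it for everyone. So the authors do write procedure-specific exclusions into 6.2, even redundant ones, and femoral nerve stimulation has no such list.

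2. **From what are people excluded?** Section 14.4 does not say. If only from the procedure, 6.2 lacks a procedure-specific list. If from the trial, 6.2 lacks a general criterion. Section 6 is incomplete either way.

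3. **Who is reached by the procedure?** Section 8.8 says volunteers in some centres. The schedules, read alone, apply the row to everyone in both arms.

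4. **How many could be exposed to the ambiguity?** The documents give no number for femoral nerve stimulation itself. If it is done in the neuromuscular sub-group (an assumption), that is 50 people. If a site follows the schedule rows as printed, it could be any of the 228 randomised, and also people familiarised at screening who are never randomised. These are numbers receiving the procedure, not numbers with hip metal or a device. The share with either is not given.

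**The case against.** The case against making much of this is good in several respects.

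- **The procedure is optional.** Under 8.8 a person unsuitable for femoral nerve stimulation can still be properly enrolled in the main study. A reader might infer that sites applying 6.2 would enrol people whom 14.4 keeps out of the trial. The documents do not support that: the sentence sits under one optional procedure and never says exclusion is from the trial. The row's baseline and 3-month timing also fits the rule for optional measures in 8.10.
- **It is not about the NMES intervention.** A reader might take 14.4 as a rule on metal near any stimulation site. NMES has its own entry, item 2, which states no metal or device exclusion, and item 4 is confined to the hip. Knee metal is therefore outside the mismatch.
- **The 6.2 list is open.** Its lead-in does not claim to be complete, so it would be wrong to say that nothing else can exclude. But an open list only permits a site to exclude more people. It also concerns contraindications to NMES therapy, so it does not clearly reach nerve stimulation.
- **The device half is weak.** The further devices in 14.4 may simply mean the defibrillator listed in 6.2. The WP1 protocol pairs the same two wordings in its sections 4.2 and 12.4. This is an unclear term, not a proven contradiction.
- **WP1 proves little.** WP1 section 4.2 excludes "The presence of metallic material in/around the hips or knees", which is wider than the RCT list. But WP1 is a separate protocol for NMES on the thigh muscles, whereas 8.8 places nerve-stimulation electrodes in the femoral triangle and at the top of the femur. Its wording cannot show that the RCT protocol contradicts itself.

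These points narrow the finding but leave the non-joint hip metal, the missing procedure list, the unstated scope and the unlabelled schedule rows.

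**Conclusion.** The concern holds in a limited form. Non-joint metal in or around the hip is excluded by 14.4 and named nowhere in section 6. The reach of the device wording in 14.4 is uncertain, and the protocol does not say whether the exclusion is trial-wide or procedure-specific. Because the schedules show the procedure unlabelled and with a screening familiarisation, its optional status in 8.8 does not fully protect against the gap.

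The finding concerns people receiving femoral nerve stimulation. It would extend to all participants only if the sponsor intends the 14.4 exclusion to be trial-wide. Its size cannot be given, because the documents contain no prevalence of such metal or devices in haemodialysis patients. It has no bearing on the primary outcome, the sample size of 228 or the analysis. It deserves correction because a safety exclusion that the protocol relies on is missing from the criteria used to screen, and the correction is cheap.

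**What to change.** Reconcile sections 6.2, 7.1, 7.2, 8.8 and 14.4:

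- Place one statement of the metal and implanted-device exclusion for femoral nerve stimulation in the eligibility section, and make 14.4 refer to it.
- Say whether it bars a person from the trial or only from that procedure.
- State which devices are meant.
- Label the femoral nerve stimulation rows in both schedules, including the screening familiarisation, to match 8.8.

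Which wording stands, and how wide the exclusion should be, is for the clinical team to decide. The cost is a wording amendment and an edit to the screening form.

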7. STUDY SCHEDULE

Visits will be broken up as the participant wishes. The 3-month follow up assessments should be carried out within 2 weeks of completing the intervention, or standard care period where possible.

It is expected that each participant will partake in the study for 10-months in total. 3-months is the end of the intervention period, 6- and 9-months are follow-up.

7.1 Schedule of procedures - NMES group

	Screening	Baseline	Each dialysis session during 3- month intervention period	Monthly	3- months	6- months	9- months
Invitation	1		•				
Eligibility assessment	1						
Informed consent		1					
Medical history		1					
Muscle strength (hand grip strength) for screening purposes and outcome assessments	1	1			1	1	1
Isometric muscle strength	1 (familiarisation session)	1			1	1	1
Isometric rate of force development	1 (familiarisation session)	1			1	1	1
Muscle size and architecture (ultrasound)		1			1	1	1
Short Physical Performance Battery		1			1	1	1
Sit to Stand 60		1			1	1	1
6-minute walk test/ISWT		1			1	1	1
Bioelectrical Impedance Analysis		1			1	1	1
EQ-5D-5L		1			1	1	1
KDQoL		1			1	1	1
SARC-F		1			1	1	1
SarQoL		1			1	1	1
GPPAQ		1			1	1	1
SONG HD - Fatigue		1			1	1	1
Resource use questionnaire and		1			1	1	1
optional diary							
Accelerometry		1			1	1	1
Sleep diary		1			1	1	1
Blood sample		1*		1 (routine clinical care)	1*	1*	1*
Neuromuscular electrical stimulation	1		1				

RPE			1				
Blood lactate				1			
measurement				I			
Heart Rate				1			
Measurement				ı			
Skeletal muscle biopsy							
– NMES group n=12		2			1		
(Optional)†							
High Density and							
Intramuscular		1			1		
electromyography		•			'		
n=25 (Optional)							
Sub-maximum	1						
contractions (for EMG	(familiarisation	1			1		
recordings)	session)						
Evoked contractions	1						
(femoral nerve	(familiarisation	1			1		
stimulation)	session)						
Capture of routine		1		1	1	1	1
clinical data^		·		'	'	'	'
Adverse event		1	1		1	1	1
assessments			ı		ı	ı	ı
Inform GP of study		1					
participation		ı					

^{*}Represents research blood samples drawn during routine clinical testing. ^Represents routinely collected serum blood results and dialysis data on all dialysis units. †In the NMES group, there is an additional biopsy after the first training session at both baseline and 3-months.

7.2 Schedule of procedures - Control group

	Screening	Baseline	Each dialysis session during 3- month intervention period	Monthly	3- months	6- months	9- months
Invitation	1						
Eligibility assessment	1						
Informed consent		1					
Medical history		1					
Muscle strength (hand grip strength) for screening purposes and outcome assessments	1	1			1	1	1
Isometric muscle strength	1 (familiarisation session)	1			1	1	1
Isometric rate of force development	1 (familiarisation session)	1			1	1	1
Muscle size and architecture (ultrasound)		1			1	1	1
Short Physical Performance Battery		1			1	1	1
Sit to Stand 60		1			1	1	1

0							
6-minute walk		1			1	1	1
test/ISWT Bioelectrical							
Impedance Analysis		1			1	1	1
EQ-5D-5L		1			1	1	1
KDQoL		1			1	1	1
SARC-F		1			1	1	1
SarQoL		1			1	1	1
GPPAQ		1			1	1	1
SONG HD - Fatigue		1			1	1	1
Resource use		 			1	1	I
questionnaire and		1			1	1	1
optional diary		'			'	'	ľ
Accelerometry		1			1	1	1
Sleep diary		1			1	1	1
Sleep dially		'		1			ı ı
Blood sample		1*		(routine clinical care)	1*	1*	1*
Neuromuscular	4			,			
electrical stimulation	1						
Skeletal muscle							
biopsy – Control group		1			1		
(n=12) (Optional)							
High-density surface and Intramuscular electromyography N=25 (Optional)		1			1		
Sub-maximum	1						
contractions (for EMG	(familiarisation	1			1		
recordings)	session)						
Evoked contractions	1 1				_		
(femoral nerve	(familiarisation	1			1		
stimulation)	session)						
Capture of routine		1		1	1	1	1
clinical data^		-		•	-	-	
Adverse event		1	1		1	1	1
assessments							
Inform GP of study		1					
participation							

^{*}Represents research blood samples drawn during routine clinical testing. ^Represents routinely collected serum blood results and dialysis data on all dialysis units.

8. RECRUITMENT

8.1 Participant identification

Potential participants will be identified by a member of the clinical team based upon the exclusion and inclusion criteria. They will be recruited via the following routes:

1) During or before a routine outpatient clinical appointment. For individuals that may be eligible to take part, participant invitation letters will be sent along with appointment letters. The clinician will formally approach the person about the study during their clinic visit and will provide the individual with an invitation letter and a brief explanation of the study. If they are interested to find out more, they will have the opportunity to speak to a member of the research team who will give them a participant information sheet and answer any questions they have. If an individual has not been identified prior to their planned clinic appointment, but the clinician deems them to be eligible they will be given the participant invitation letter together with the participant information sheet and a brief explanation of the study. If they are interested, they will then be given the opportunity to speak to a member of the research team;

2) During a dialysis session or ward round on the unit. The clinician will speak to the individual either as part of a normal ward round, or as a separate initial approach about STIM-HD. They will provide the individual with an invitation letter and the participant information sheet, and provide a brief explanation of the study. If they are interested to find out more, they will have the opportunity to speak to a member of the research team who will answer any questions they have.

8.2 Screening and eligibility assessment

Potential participants will be screened for eligibility by a member of the clinical team using their most recent laboratory tests and medical history.

8.3 Consent

Potentially eligible participants will be initially approached by a member of their usual healthcare team to see if they would like to take part in the study. Patients will be provided with a PIS to take home, or this can be emailed to them. A member of the research team will speak to them a few days later to discuss the exact nature of the study, the implications and constraints of the protocol, and any risks involved in taking part, at a time convenient for the patient, most likely whilst they are receiving dialysis to answer any further questions and to confirm their decision regarding participation. They will be given as much time as they wish to consider their participation and the opportunity to question their GP or other independent parties. If the individual would like to take part, the research team will then organise a suitable time for them to sign the consent form and to complete the assessments. The PIS will clearly state that the participant is free to withdraw from the study at any time for any reason without prejudice to future care, and with no obligation to give the reason for withdrawal.

The participant must personally sign and date the latest approved version of the informed consent form before any study specific procedures are performed. Written Informed Consent will be obtained by means of a signed and dated up to date version of the consent by both the individual taking part, and the person who presented and obtained the informed consent. The person who takes consent will be suitably qualified and experienced, and will have been authorised to do so by the Chief/Principal Investigator as detailed on the Delegation of Authority and Signature log for the study.

The original signed consent forms will be retained at each study site within the Investigator Site File (ISF) together with a copy of the relevant information sheet. A copy of the signed Informed consent will be given to participants a copy retained in the participant medical notes, and a copy retained for sample transfer.

